Module 4: Sleep hygiene and stimulus control: Information on sleep-inhibiting substances, sleep-wake-rhythm, evening rituals, physical exercise, etc., as well as information on the principle of stimulus control with the aim of re-associating the bed with sleep.

Module 5: Progressive Muscle Relaxation (PMR) based on Jacobson with audio tape and written instruction to download.

Module 6: Cognitive restructuring: Identifying, reexamining and changing dysfunctional thoughts about sleep and the consequences of insomnia.

Module 7: Relapse prevention: what to do to prevent sleep disorders or when the sleep disturbances come back, when to seek medical help and what are the conditions of safe pharmacotherapy for insomnia.

Module 8: Repetition and end.

The program includes a sleep diary in which participants insert data on their bedtime and waketime, sleep latency, total sleep time, and night awakenings. The data entered into the sleep diary are then presented in form of graphs. Furthermore, various exercises serve to put what is learnt into practice. Participants have time to repeat, deepen and apply modules, exercises and examples in their everyday life at their own pace, i.e., the

participants are free to choose when and how often they process the modules and whether they process them in one piece or in several stages. Patients will get behavioral instructions based on their questionnaires, sleep diary, and answers in the interactive part of the program. A sleep window will be proposed depending on the preferred wake-up time and average total sleep time over the last 7 days. If the sleep diary indicates a sleep efficiency of 85% or higher for the previous week, the participant will be encouraged to add 15 min to the sleep window. If it does not reach the 85%, recommended sleep window will be decreased based on the preferred wake-up time and average total sleep time over the period of observation. If the sleep efficiency falls between 80% and 85% sleep window will remain stable otherwise (sleep efficiency > 85%) it can be extended by 15 min. All material will be delivered through the internet program and expected to be elaborated by the patients themselves but with the opportunity to contact a psychologist or somnologist within the program (guidance on request) in a secured environment

The program was elaborated by [name], M.D., Ph.D., associate professor, Sechenov university. M.D., D. [name], M.D., Ph.D. [name].

Owner and producer of iCBT-I course “Sleepsy” is LLC Technomarkt, Medical license № ЛО-77-01-015518 22.01.2018.

4.1. CONCURRENT THERAPY

Both groups will have access to CAU. Interventions that are part of CAU may be assigned within the first visit to a referring doctor or at any point of the study on a next doctor visit. All concurrently applied treatments will be assessed repeatedly by self-report.

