- 11) User Satisfaction. After completion of the iCBT-I course participants will be requested to fill in feedback questionnaire developed for this study. It includes 5-point Likert scale, from 1 (very poor/not at all useful) to 5 (very, good/very useful) on questions about satisfaction or dissatisfaction with the treatment, and open questions about possible negative effects of the intervention if any: deterioration of insomnia symptoms, adverse effects, novel symptoms; and about improvement suggestions, what participants like most, if they would recommend it to a friend with insomnia.
- 12) The System Usability Scale (SUS) is the 10-item non-specific questionnaire used to collect a user's subjective rating of a product's (products, websites, applications, hardware, or software) usability and learnability. Each item is scored on a scale of 0 ("strongly Disagree") to 5 ("strongly Agree").
- 13) General information will be requested at baseline: age, sex, education, social status, duration of CI, sleep aids if any.

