4.2.1. RESTRICTED CONCURRENT THERAPY

not applicable

5. SAMPLE SIZE.

110 patients with CI will be recruited through referrals from health care practitioners, i.e., neurologists specialized in somnology.

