8. SAFETY ASSESSMENT

8.1. SAFETY ASSESSMENT MEASURES

The referring specialists will explain to each participant the nature of the study, its purpose, the procedures involved, the expected duration, the potential risks and benefits and any discomfort it may entail, voluntary participation, withdrawal from the study at any time and that withdrawal of consent will not affect his or her subsequent medical assistance and treatment. After eligibility assessment, potential participants will receive a participant information sheet and a consent form. The informed consent (IC) is compiled in accordance with the National Standard of the Russian Federation for Clinical investigations and good clinical practice (GOST R ISO 14155- 2014) for the creation of an IC for information transfer. Each participant will have seven days to decide whether to

participate or not. After returning the signed IC, each participant will receive a copy of the IC signed by the authorized investigator.

The investigated method is not associated with serious adverse events. In order to avoid severe tiredness we have chosen more lenient minimal time in bed of 6 h. In the program, the caution to avoid severe sleep deprivation is made for elderly patients and for those who have duties in which drowsiness may be a danger to the patients themselves or others. These patients are recommended to flexibly extend sleep window.

8.2. RISKS FOR WOMEN OF CHILDBEARING POTENTIAL.

None

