9.2. STATISTICAL ANALYSIS OF EFFECTIVENESS

The main analyses will be conducted on the intention-to-treat sample. Clinical effects of treatment will be evaluated using mixed-model repeated-measures analyses where the pre-post comparisons of all outcome measures will include time as a within-group variable and the condition as a between-group variable. An incremental cost-effectiveness ratio (ICER) will be calculated to obtain the additional costs of iCBT-I in comparison with control condition. Cohen's d will be reported for all within-between comparisons based on estimated means and the pooled standard deviation from the observed means at pre- and posttreatment. To test significance of the difference between the number of responders in each treatment condition, we will use χ^2 -test. Regression analyses will be used to identify predictors of treatment outcome. We will test models using Akaike/Bayesian Information Criteria to select an optimal model with predictors of treatment outcome.

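### Usual care newly started at the referral visit is not identified at T0 and has no stated place in the uncontrolled predictor regression, so its effect can be counted as iCBT-I benefit

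*Combined protocol and SAP*

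**What the plan says.** Section 4.1 (Concurrent therapy) allows usual care (CAU) in both arms: "Interventions that are part of CAU may be assigned within the first visit to a referring doctor", and also at later visits. Section 4.2.1, on restricted concurrent therapy, reads "not applicable", and the eligibility criteria in 7.1 and 7.2 do not ask for stable treatment. After the referring specialist has explained the study, 8.1 states that "Each participant will have seven days to decide". Under section 3, signed consent triggers the e-mail link, the online baseline (T0) follows, and randomisation comes last.

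Three sources on concurrent treatment are described:
- Section 4.1: "All concurrently applied treatments will be assessed repeatedly by self-report".
- Section 3.1.2, item 13: "General information will be requested at baseline: age, sex, education, social status, duration of CI, sleep aids if any".
- Section 3.1.2, item 8: the TiC-P, which covers the name, dose and frequency of insomnia medication and is given at T0 and every later assessment (section 3.2).

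None of these is described as recording a start date.

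For the analysis, 9.2 gives the mixed model two factors, time and condition. On aim 2 it says "Regression analyses will be used to identify predictors of treatment outcome", with the model chosen by AIC/BIC and no covariates listed. Section 9.1 places that analysis among participants who complete iCBT-I, enlarged by control participants treated after the follow-up.

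**The concern.** T0 mixes patients who have just begun a new insomnia treatment, patients on long-standing treatment and patients on none. Long-standing treatment is already reflected in the T0 ISI. A treatment begun a few days earlier will have most of its effect between T0 and T1, in the same window as iCBT-I.

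In the randomised comparison both arms carry this equally on average. In the predictor analysis nothing subtracts it. For a patient in the immediate iCBT-I group, the T0 to T1 change is iCBT-I plus whatever the newly started care contributes. Any characteristic that makes a doctor more likely to prescribe at referral can then look like a characteristic that predicts iCBT-I benefit. Aim 2 is a stated aim, and the background section intends its result to guide individual treatment decisions. The profile of who benefits could partly be a profile of who was given something new at referral.

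**Working it through.** **1. Order of events.** Referral visit with possible new CAU (4.1), up to seven days to decide (8.1), consent, T0, randomisation (section 3). A new start at referral is therefore a pre-randomisation characteristic, but a very recent one.

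**2. The plan's own figure.** Section 9.1 gives d = 0.35, alpha 0.05, power 0.95 and N = 110. A repeated-measures ANOVA, within-between interaction, with f = d/2 = 0.175, m = 2 time points and an assumed correlation of 0.5 (not stated in the plan) has noncentrality f² × N × m/(1 − rho) = 0.175² × 110 × 2/0.5 = 13.475. Power is 0.953, so 110 reproduces.

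**3. Effect on the randomised contrast.** The documents give neither the share p starting new CAU nor its effect e. Assume p = 0.3 to 0.5, e = 2 to 4 ISI points, and a residual SD of change of 5, with 55 per arm.
- Added variance of change is e² × p(1 − p): 4 × 0.21 = 0.84 at the low end, 16 × 0.25 = 4 at the high end.
- The 95% half-width without it is 1.96 × √(2 × 25/55) = 1.87 points.
- With it: 1.96 × √(2 × 25.84/55) = 1.90 points, or 1.96 × √(2 × 29/55) = 2.01 points.
- Ratios: √(25.84/25) = 1.02 and √(29/25) = 1.08, so 2% to 8% wider.

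On the power scale, with p from 0.2 to 0.7 and an effect of 0.25 to 1.0 SD, the variance factor 1 + p(1 − p) × effect² is 1.01 to 1.25. Power at N = 110 falls from 0.953 to between 0.952 and 0.902.

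**4. Effect on the predictor regression, immediate group only.** Assume n = 55, p = 0.4, e = 3, SD 5, and a trait with no true effect whose correlation with new CAU is r.
- Mean change wrongly counted as iCBT-I change: 0.4 × 3 = 1.2 points.
- Spurious slope per SD of the trait: r × e × √(p(1 − p)) = 0.3 × 3 × 0.49 = 0.44 at r = 0.3, and 0.5 × 3 × 0.49 = 0.73 at r = 0.5.
- Simulated false-positive rate at p < 0.05: about 9% (r = 0.3) and 17% (r = 0.5). At the threshold implied by AIC for one term (p < 0.157, nominal 15.7%): about 23% and 35%.
- At r = 0.1 the rate at p < 0.05 is about 5%.
- With a new-CAU term in the model the rates return to about 5% and 15%.

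**5. Delayed controls added.** Controls start iCBT-I after week 20, when care begun at referral is about five months old. Assume 45 of them, with no remaining effect of that care on their change during iCBT-I. The spurious slope is diluted by 55/100, to 0.44 × 0.55 = 0.24 and 0.73 × 0.55 = 0.40. False positives at p < 0.05 are about 7% (r = 0.3) and 12% (r = 0.5).

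**6. Form of an adjustment in the ISI model.** With pre and post ISI as repeated outcomes and complete data, a covariate that is constant over time is orthogonal to within-person change. In a simulated trial with a 4-point CAU effect, the time-by-condition estimate was −1.230 (SE 0.922) both with and without the main effect. Adding covariate-by-time gave −1.461 (SE 0.833). Only the interaction does anything.

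**The case against.** **CAU is part of the design.** The comparison is iCBT-I plus CAU against CAU alone, and 9.1 chose the effect size with an active CAU in mind. This stands. A reader might infer that newly started care biases the primary result. The documents do not support that: starts before T0 are balanced in expectation by randomisation. A 95% chance imbalance could move the estimate by 1.96 × √(2 × 0.21/55) × 2 = 0.34 to 1.96 × √(2 × 0.25/55) × 4 = 0.75 points, but the standard error already covers this. The planned SD may also already contain this variation.

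**The plan does collect treatment data, and its predictor list is open.** This stands too. A reader might infer that CAU is ignored at T0 or left out of the regression. In fact sleep aids and TiC-P medication data are taken at T0, and 9.2 names no predictors at all. The role of CAU is unspecified, not shown to be omitted. The instruments are only summarised, so it cannot be excluded that one of them holds a start date. What remains is that no described item separates new from long-standing use, and no rule says how these data enter the regression.

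**The numbers are assumed and the cure is partial.** The share, effect and correlation have no source in the documents, and weak correlations do no material harm. The return to nominal error rates holds by construction, because new CAU was the only confounder simulated. Care started at later visits, natural course and regression to the mean would remain. This is a fair limit on what the fix achieves, but it does not justify leaving out a cheap partial control.

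**Conclusion.** The point holds for aim 2 and is minor for the primary endpoint. The randomised ISI contrast is unbiased, and its interval would be about 2% to 8% wider under a 30% to 50% share and a 2 to 4 point effect. In the predictor analysis, change due to newly started CAU in the immediate group is counted as iCBT-I change, and prescribing-related traits can pass as predictors. With 40% new CAU worth 3 points, SD 5 and a trait correlation of 0.3 to 0.5, false positives at p < 0.05 are about 9% to 17% in the 55 immediate patients and about 7% to 12% with 45 delayed controls added. At correlation 0.1 the inflation is negligible. The gap in the text is clear; its size in this trial is unknown, because the documents give none of these inputs.

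**What to change.** - **T0 questionnaire:** for each current insomnia treatment, ask whether it was started at or after the referral visit (yes/no) and the start date. If this is not asked at T0, it can be recovered later only by recall.
- **Section 9.2, predictor regression:** force in a term for new CAU before T0, set to apply to the immediate group, together with an indicator of immediate versus delayed treatment. Do this before AIC/BIC selection begins. Use only starts before T0, so that nothing arising after randomisation is conditioned on.
- **Section 9.2, ISI mixed model (optional, for precision):** add new CAU and its interaction with time. A main effect alone leaves the treatment estimate unchanged.
- **Stated limitation:** say that CAU started later, natural course and regression to the mean are not separated from iCBT-I in the predictor analysis, because it has no comparator.

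The cost is one extra baseline item, some wording, and one or two degrees of freedom. Care, visits and sample size do not change.

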4.2.1. RESTRICTED CONCURRENT THERAPY

not applicable

5. SAMPLE SIZE.

110 patients with CI will be recruited through referrals from health care practitioners, i.e., neurologists specialized in somnology.

7.1. INCLUSION CRITERIA

1. Age between 18 and 80 years
2. Sleep disorder matching CI criteria (International Classification of Sleep Disorders-3) — assessed by clinical judgement
3. Ability to follow the procedures of the study, fluent Russian language, good access to internet — assessed by self-report

7.2. NON-INCLUSION CRITERIA

1. Presence of dementia (identified by history or a score < 25 on the Folstein Mini Mental Status Exam) — assessed by clinical judgement.
2. Severe depression or severe anxiety as measured with the Beck Depression Inventory (BDI-II; score > 28) and the Beck Anxiety Inventory (BAI; score > 25)—assessed by the questionnaires.
3. History of severe psychiatric comorbidities other than anxiety and depression (bipolar disorders, psychotic disorders) or substance use disorder—assessed by self-report and clinical history.
4. Untreated severe obstructive sleep apnea syndrome (apnea-hypopnea index [AHI] > 15), restless legs syndrome (movement index with arousal > 15 per hour) or other sleep disorders affecting night sleep—assessed by clinical judgement and clinical history.
5. Pregnancy, lactation—assessed by self-report.
6. Having a serious somatic condition or brain disorders (stroke, Parkinson's disease, etc.) preventing further participation—assessed by self-report.
7. Having high suicidality risk—assessed by clinical judgement, high total BDI-II score (>28) or score >1 on a BDI-II of suicidality subscale.

7.3. EXCLUSION CRITERIA

1. Refusal of the further participation;
2. Pregnancy
3. Exacerbation of Anxiety or depressive disorder as measured with the Beck Depression Inventory (BDI-II; score > 28) and the Beck Anxiety Inventory (BAI; score > 25)—assessed by the questionnaires at any timepoint
4. Increase of suicidality risk — as measured with BDI-II suicidality subscale score >1 at any timepoint

8. SAFETY ASSESSMENT

8.1. SAFETY ASSESSMENT MEASURES

The referring specialists will explain to each participant the nature of the study, its purpose, the procedures involved, the expected duration, the potential risks and benefits and any discomfort it may entail, voluntary participation, withdrawal from the study at any time and that withdrawal of consent will not affect his or her subsequent medical assistance and treatment. After eligibility assessment, potential participants will receive a participant information sheet and a consent form. The informed consent (IC) is compiled in accordance with the National Standard of the Russian Federation for Clinical investigations and good clinical practice (GOST R ISO 14155- 2014) for the creation of an IC for information transfer. Each participant will have seven days to decide whether to

participate or not. After returning the signed IC, each participant will receive a copy of the IC signed by the authorized investigator.

The investigated method is not associated with serious adverse events. In order to avoid severe tiredness we have chosen more lenient minimal time in bed of 6 h. In the program, the caution to avoid severe sleep deprivation is made for elderly patients and for those who have duties in which drowsiness may be a danger to the patients themselves or others. These patients are recommended to flexibly extend sleep window.

8.2. RISKS FOR WOMEN OF CHILDBEARING POTENTIAL.

None

8.3. RISKS FOR MEN OF REPRODUCTIVE ABILITY

None

8.4. UNDESIRABLE EVENTS AND UNDESIRABLE EFFECTS OF THE METHOD UNDER INVESTIGATION

We will assess depressive and anxiety symptoms with the BDI and BAI as a safety outcome at all times of data collection, i.e., as part of the initial screening, during and after the intervention, as well as at the follow-up measures. Severe depression and anxiety are defined as BDI-II scores > 28 and BAI scores > 25 , accordingly. If scores are higher than these cutoffs at the time of the screening, the person concerned will not be admitted to participate in the study and will be referred to a suitable authority such as a psychotherapist, a psychiatric clinic, or a hospital. Should this occur during another time throughout the study, participants will also be given information on suitable institutions to turn to and asked to inform the contact person for emergencies named by them at the beginning of the study. Furthermore, participants receive a weekly individualized automated e-mail during the intervention, acknowledging their progress and offering help if they encountered difficulties with the program. Persons who had to be directed to psychiatric/psychotherapeutic services will be contacted by the study team as soon as possible to assure that they are in professional care.

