8.5. SUBSEQUENT MONITORING AFTER SERIOUS ADVERSE EVENTS

In the case of serious adverse events causing drop-out of a participant. This participant will be directed to psychiatric/psychotherapeutic services will be contacted by the study team as soon as possible to assure that they are in professional care. Subsequent monitoring of participants completed the study or dropped out is not provided.

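### A BDI-II suicidality score above 1 bars entry or excludes, but on its own it does not trigger the referral and information steps in section 8.4

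*Combined protocol and SAP*

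**What the plan says.** Section 8.4 uses the BDI-II and BAI as safety measures, collected "as part of the initial screening, during and after the intervention, as well as at the follow-up measures". It fixes the thresholds: "Severe depression and anxiety are defined as BDI-II scores > 28 and BAI scores > 25". At screening, "If scores are higher than these cutoffs at the time of the screening, the person concerned will not be admitted to participate in the study"; that person is referred to a psychotherapist, clinic or hospital. Later on, "Should this occur during another time throughout the study, participants will also be given information on suitable institutions to turn to", with a request that they inform their named emergency contact. A further sentence provides that "Persons who had to be directed to psychiatric/psychotherapeutic services will be contacted by the study team as soon as possible".

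Suicidality has its own criterion in the eligibility sections. Section 7.2 item 7 bars entry for "Having high suicidality risk—assessed by clinical judgement, high total BDI-II score (>28) or score >1 on a BDI-II of suicidality subscale". Section 7.3 item 4 excludes a participant for "Increase of suicidality risk — as measured with BDI-II suicidality subscale score >1 at any timepoint". Neither item states a referral or a contact.

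Section 8.5 has a separate route, which opens "In the case of serious adverse events causing drop-out of a participant". That participant is sent to mental health services and contacted by the team. The section closes by saying that people who have completed or left the study are not monitored further.

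**The concern.** The protocol treats the suicidality score as a danger signal separate from the BDI-II total: it is joined by *or* in 7.2 item 7 and stands alone in 7.3 item 4. Section 8.4, which says what is done for a person in difficulty, mentions only the two totals. A site that follows 8.4 exactly could turn away or remove someone flagged for suicidality without the steps it must take for severe depression or severe anxiety.

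A written trigger matters more here because contact is largely remote. Questionnaires are completed online under a code (section 3). Identifying a participant means matching code to email and email to consent form (section 15). The assessment schedule in 3.2 lists no clinic visit at T1 or T2. A flagged score therefore need not come up in front of a clinician.

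**Working it through.** No figure in the plan needs reproducing; the check sets the criteria beside the stated responses. It assumes that either cutoff alone triggers 8.4, which is the reading most favourable to the protocol.

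| Finding | At screening | On study |
|---|---|---|
| BDI-II > 28 | Not admitted (7.2 items 2 and 7); referred (8.4) | Excluded (7.3 item 3); institution information and emergency-contact request (8.4) |
| BAI > 25 | Not admitted (7.2 item 2); referred (8.4) | Excluded (7.3 item 3); same 8.4 steps |
| Suicidality score > 1, with BDI-II ≤ 28 and BAI ≤ 25 | Not admitted (7.2 item 7); no referral stated | Excluded (7.3 item 4); 8.4 not triggered; services and contact only if 8.5 is read to apply |

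*Can the third row occur?* Section 3.1.2 item 4 gives the BDI-II 21 questions scored 0 to 3, so the total runs from 0 to 21 × 3 = 63. A suicidality score above 1 is at least 2. The 8.4 trigger needs a total of at least 29. A score of 2 leaves 28 − 2 = 26 points that the other answers can add before 8.4 is reached. The case is therefore possible, and the two criteria are distinct. This says nothing about frequency.

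*Does 8.5 close the on-study gap?* Two links would have to hold: a suicidality score above 1 counts as a serious adverse event, and exclusion under 7.3 item 4 counts as drop-out caused by it. The text states neither, and section 8.1 says that the method has no association with serious adverse events. If a site does not make both links, the closing sentence of 8.5 applies and no monitoring follows.

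*Does 8.5 help at screening?* No. It concerns participants who drop out, and a person refused entry is not one.

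*Do other provisions supply a trigger?*
- Usual care is open to both groups (4.1), but visits are not tied to scores.
- The centre helps with the baseline online assessment (10.1), but nothing there says that anyone reviews the BDI-II answers.
- In-program contact with a psychologist or somnologist is on request (section 4), so it starts with the patient. Controls have no program access until after the 5-month follow-up (section 3).
- The weekly e-mails in 8.4 offer help with difficulties in using the program.
- Adverse events are documented, notified to the principal investigator and reported to the ethics committee (8.4.1, 10.1). That is reporting, not handover to care.

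**The case against.** The strongest reply concerns the on-study half. Section 8.5 sends people to mental health services, a destination that fits psychiatric reasons for leaving, and 7.3 items 3 and 4 are the psychiatric reasons in the protocol. Reading item 4 into 8.5 is natural. Where 8.5 applies, it is also stronger than the on-study step in 8.4, which gives information rather than a referral. This stands: on study the problem is an ambiguity, not an absence.

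A reader might infer that the study-team contact in 8.4 is reserved for people above the two cutoffs. The documents do not support that. "Persons who had to be directed to psychiatric/psychotherapeutic services will be contacted by the study team as soon as possible" names no score, so anyone directed to services by another route also fits. What is missing is a stated route by which the suicidality score leads to being directed.

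A reader might also infer that the suicidality score goes unread. It does not: 7.3 item 4 cannot be applied without checking it.

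At screening, the reply is that the gap is narrow. One branch of 7.2 item 7, BDI-II above 28, is already referred under 8.4. The clinical-judgement branch already involves a clinician, who needs no script for responding to their own judgement. Patients also come through neurologists (section 5). These arguments limit the gap to the score-only branch but do not remove it: the sponsor wrote the step out for severe depression and anxiety and left it out for this score.

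**Conclusion.** The concern holds in this form. At screening, a suicidality score above 1 with both totals at or below their cutoffs leads to refusal of entry and, in the available text, to no stated referral. On study it leads to exclusion, with handover to care only if 8.5 is read to cover it. The plan should be corrected, because a site applying the written cutoffs faithfully would omit the handover.

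The number of people affected cannot be derived from the documents, and it would be wrong to infer from the overlap of possible scores that the gap is common. Nor do the documents support the conclusion that such people would get no help: ordinary clinical care, 8.5 and adverse event reporting may each reach them. None of these is a written trigger tied to the score.

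The conclusion rests on two assumptions: that either cutoff alone triggers 8.4, and that the parts of the document not available for this review, one of which lies between section 5 and section 7.1, contain no such instruction.

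**What to change.** In 8.4, add *or BDI-II suicidality score > 1* to the trigger, at screening and at every later BDI-II assessment, whatever the BDI-II and BAI totals. In 8.5, state that a participant excluded under 7.3 item 4 is directed to services and contacted by the study team before the sentence ending further monitoring applies. The clinical content of the response is for the sponsor and the ethics committee to set.

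The cost is a wording change in two sections and an unknown, probably small, number of extra study-team contacts. No new data collection or score check is needed, because the score is already collected and must already be checked under 7.3 item 4.
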